6.3.4 Concomitant therapy

Patients will be instructed not to take any additional medications (including over-the-counter products) during the course of the study without prior consultation with the investigator. At each visit, the investigator will ask the patient about any new medications he/she is or has taken after the start of the study drug.

All Concomitant medications/Significant non-drug therapies taken ≤ 30 days prior to start and after start of study drug, including physical therapy and blood transfusions, should be recorded.

The use of concomitant medications that might lead to QT prolongation (appendix A) is prohibited and requires the discontinuation of the patient prior to starting the respective QT prolonging medication.

Pasireotide is a moderate inhibitor of CYP2C9 and 2D6. Substrates of CYP2C9 and 2D6 (appendix D) with a narrow therapeutic index should be used with caution. Patients on Warfarin should have their INR monitored more closely while receiving SOM230.

6.3.5 Study drug discontinuation

Patients experiencing unacceptable toxicity (AE grade 3 or higher) that the investigator considers directly attributable to the study drug should have their dose adjusted as per dose modification guidelines in Table 6-2. If a patient has already decreased 1 dose level, no further dose reduction is permitted, and the patient will be permanently discontinued from treatment. For QTc related protocol discontinuation, please see section 6.3.2. For LFT related protocol discontinuation, see section 6.3.3.

6.4 End of treatment

Patients may voluntarily withdraw from the study or be dropped from it at the discretion of the investigator at any time. Patients will be withdrawn from the study if any of the following occur:

- Disease progression
- Death
- Withdrawal of consent
- Delay of treatment >21 days.
- Uncontrolled diabetes mellitus (DM)
- Pregnancy
- Adverse event(s) \geq grade 3 despite dose reduction
- QTc prolongation (see section 6.3.2)

7 Visit schedule and assessments

7.1 Pretreatment Evaluation

Baseline tumor and patient characteristics including:

- Patient demographics: age, gender and race (Caucasian, Black, Hispanic, Asian, other).
- Medical history
- Medications
- ECOG performance status.
- Type of neuroendocrine tumor: primary site (if known) vs. unknown.
- Differentiation or grade (if available).
- Known sites of metastases.
- Estimation of tumor burden in the liver (none vs. <10% vs. >10%).
- Presence or absence of radiotracer uptake on OctreoScan (if available).
- Presence or absence of hormonal syndrome (carcinoid syndrome, gastrinoma syndrome, insulinoma syndrome, etc.)
- Presence or absence of a pathologically elevated hormone or biomarker.
- EORTC QLQ C-30 and EORTC QLQ GI-NET21 questionnaires

Tests to be performed within 28 days prior to initiation of therapy (if day 28 falls on a weekend or holiday the deadline may be extended to the next working day):

- Radiologic assessment of tumor burden by CT scan or MRI
- Assessment of secretory proteins. All patients will undergo an initial assessment of chromogranin A. Patients with suspected serotonin-producing tumors (and all patients with midgut carcinoid tumors) will have a 24 hour urine 5-HIAA measured at

baseline. Other possible neuroendocrine tumor markers/hormones (e.g. pancreatic polypeptide, gastrin, glucagon, etc.) may be collected at the discretion of the investigator based on clinical symptoms and tumor location.

Tests to be performed within 14 days prior to initiation of therapy (if day 14 falls on a weekend or holiday the deadline may be extended to the next working day):

- History and physical evaluation including height, weight, vital signs and performance status.
- Baseline hematological and biochemical profiles including CBC with differential and comprehensive metabolic panel (fasting glucose, sodium, potassium, chloride, bicarbonate, creatinine, blood urea nitrogen, albumin, SGOT (AST) SGPT (ALT) total bilirubin, alkaline phosphatase, calcium and magnesium).
- Hemoglobin A1c
- Serum pregnancy test for women of childbearing potential
- Electrocardiogram

7.2 Evaluations During Treatment

Beginning of every cycle (defined as 28 days +/- 3 days) (every 6 months after 5 years on therapy)

- Physical examination
- Toxicity assessment
- Vital signs
- ECOG performance status
- CBC with differential
- Fasting comprehensive metabolic panel
- Assessment of adverse events

Data to be obtained every 3 cycles of treatment (every 12 months after 5 years on therapy):

- Radiologic assessment of tumor burden by CT scan or MRI. Patients who have been on study for > 2 years will undergo scans every 6 cycles. Patients who have been on study for > 5 years will undergo scans every 12 cycles, at treating physician discretion.
- Electrocardiogram (baseline, 6 hours after 1st injection, 21 days after 1st injection, 21 days after 3rd injection, Cycle 6, and every 3 cycles thereafter.)
- Liver function testing 21 days after 1st injection and 21 days after 3rd injection
- Assessment of chromogranin A and/or other tumor markers or hormones if elevated at baseline (see section 7.1).
- EORTC QLQ C-30 and EORTC QLQ GI-NET21 questionnaires

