4.1 Treatment

The investigational drug used in this study is pasireotide LAR 60mg. Pasireotide will be administered as an intramuscular injection at the beginning of every cycle which is defined as 28 days (+/- 3 days). Study treatment should begin within 14 days following enrollment into the study and continue until disease progression, unacceptable toxicity, or withdrawal of consent. Safety and efficacy will be assessed throughout the treatment period.

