6.3 Follow-up for toxicities

Patients who interrupt or permanently discontinue pasireotide due to an adverse event or abnormal laboratory value must be followed at least weekly for 28 days after the last dose of pasireotide, and subsequently at monthly intervals until resolution or stabilization of the event,

whichever comes first. If a patient requires a dose delay of > 21 days from the intended day of the next scheduled dose, then the patient should be discontinued from the study.

All patients will be followed for adverse events and serious adverse events for 28 days following the last dose of pasireotide.

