6.3.3 Management Guidelines for Abnormal Liver Function

Table 6-3-3: SOM230 Abnormal liver function management

Perform within **72 hours** of awareness of abnormal LFTs:

- Perform liver-directed medical history and physical examination (i.e. assess occupational hazards, concomitant medications including OTC meds, intercurrent illness, etc)
- Liver chemistry tests: ALT, AST, total bilirubin, (fractionate to direct/indirect bilirubin if total bilirubin is $> 2.0x$ ULN), Alb, PT (INR), ALP, and GGT
- Perform hepatitis screen: anti-HAV, IgM (to confirm acute hepatitis A), HbsAg, Anti-HBc, anti-HCV (if positive PCR viral load should be assessed), Anti-HEV, ANA antibodies, anti-smooth muscle anti-bodies, CMV, EBV
- Perform abdominal ultrasound (liver and biliary tree)
- Collect PK sample and record the dose level and the dosing time for the last dose the patient has taken prior to PK sampling.

Liver chemistry tests should be monitored **every 3-4 days** for s.c. and LAR studies until resolution or return to baseline status.

For ALT or AST > 5x ULN and ≤ 8x ULN:

Study medication should be temporarily interrupted and liver chemistry tests monitored **every 3-4 days** for s.c. and LAR studies until resolution or return to baseline

If resolution or return to baseline does not occur after 2 weeks, the patient should be discontinued.

If ALT or AST returns to less than 5x ULN, study drug can be resumed and patient can continue study per protocol

If ALT or AST rises above 5x ULN anytime after study drug is resumed, then study drug should be discontinued immediately.

Table 6-3-3-1: SOM230 Abnormal liver function discontinuation criteria Hepatic-related discontinuation criteria for all ongoing studies

Study medication should be discontinued immediately if any of the discontinuation criteria below are met:

ALT or AST > 3x ULN and Total Bilirubin > 2x ULN and ALP < 2x ULN

ALT or AST > 5x ULN and ≤ 8x ULN persistent for more than 2 weeks

ALT or AST > 8x ULN

Re-challenge of study medication is prohibited once discontinuation criteria are met.

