^e Comprehensive metabolic panel should include fasting glucose, sodium, potassium, chloride, bicarbonate, creatinine, blood urea nitrogen, albumin, total protein, SGOT (AST), SGPT (ALT), total bilirubin, alkaline phosphatase, calcium and magnesium. Patients are to fast overnight for 8 hours prior to all biochemistry samples being taken. Blood samples are to be taken in the morning. Water is allowed during this time. Clinically significant electrolyte abnormalities are to be addressed prior to each SOM230 administration.

^f For women of child-bearing potential: Women of childbearing potential must have a negative serum pregnancy test within 14 days of enrollment. Acceptable contraception must be used while on study and for at least 60 days after last dose of pasireotide.

^g If patients present with hormonally active tumor, secretory hormone levels corresponding to the syndrome (e.g. urine 5-HIAA, gastrin, glucagon, insulin, etc.) should be measured at baseline and each restaging cycle.

^h Baseline radiologic tests (CT or MRI with iv contrast) should include all known sites of metastatic disease. For most midgut carcinoid tumors, a CT or MRI scan of the abdomen and pelvis is indicated. For pancreatic neuroendocrine tumors, a CT or MRI scan of the abdomen may be sufficient. Patients who have been on study for > 2 years will undergo scans every 6 cycles. Patients who have been on study for > 5 years will undergo scans every 12 cycles.

ⁱ See section 9.1 for definitions of adverse events

^j All concomitant medications, including over the counter drugs, should be documented each visit. Particular attention should be paid to dose of diabetic medications. Patients with diabetes are to be instructed to check blood glucose levels via a fingerstick several times daily, particularly for the first few days of treatment.

^k For patients who have been on study for >5 years, all procedures, with the exception of vitals and treatment administration, will occur only once every 6 months (EP, labs, EKGs, questionnaires); scans will occur once every 12 months.

8 Outcome Measures

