The primary efficacy endpoint is progression-free survival, defined as the time from the date of first study treatment to the date of the first documented disease progression (by RECIST criteria) or death due to any cause. If a patient has not progressed or died at the date of the analysis cut-off or when he/she receives any further anti-cancer therapy, PFS is censored at the time of the last tumor assessment before the cut-off or the anti-cancer therapy date.

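### Tumour scans follow treatment cycles rather than calendar time, so scan dates and recorded PFS drift with injection delays; the 12-month rate is biased upward only when total slip exceeds 29 days

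*Combined protocol and SAP*

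**What the plan says.** Section 7.2 places CT or MRI under "Data to be obtained every 3 cycles of treatment (every 12 months after 5 years on therapy", and Table 7-3 uses the same three-cycle column. Section 4.1 gives the injection "at the beginning of every cycle which is defined as 28 days (+/- 3 days", so the injection starts the cycle. For later years, footnote h of Table 7-3 says "Patients who have been on study for > 2 years will undergo scans every 6 cycles". Calendar timing appears only beyond five years on study, where 12 months (section 7.2, footnote k) stands beside 12 cycles (section 7.2, footnote h).

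Section 6.3 states when a late dose ends participation: "If a patient requires a dose delay of > 21 days from the intended day of the next scheduled dose". Section 6.4 repeats the limit as "Delay of treatment >21 days". Shorter delays are tolerated, and no section caps how many a patient may have. For one band of liver-enzyme elevation, section 6.3.3 says "Study medication should be temporarily interrupted and liver chemistry tests monitored".

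Section 8 has PFS "defined as the time from the date of first study treatment to the date of the first documented disease progression", or to death. Section 8.4 acknowledges that true progression lies somewhere between two scans, and Table 8.4 dates radiologic progression to an assessment. Section 11.2 makes the 12-month PFS rate the primary endpoint of a single-arm trial, with a null of 19%, an alternative of 40% and one-sided alpha of 10%. No section says which scan, or what window, supplies the month-12 status.

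**The concern.** A site that follows the text moves the scan whenever it moves the injection. Two patients whose tumours progress on the same day can then be given different PFS times because one had a late dose. Table 8.4 does not correct this: its rules concern missed visits, and a scan that moves with its cycle has not been missed. With no control arm, the drift cannot cancel between groups, and the comparison is with a fixed external rate.

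Two quantities are at stake. One is the PFS distribution, which section 3.1 also lists as primary. The other is the 12-month rate, which depends on the last scan taken on or before month 12.

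**Working it through.** **Inputs.** Scan every 3 cycles of 28 days (4.1, 7.2). Delay of up to 21 days per dose (6.3, 6.4). Null 19%, alternative 40%, medians 5 and 9 months, n=30, one-sided alpha 10%, power 90% (11.2). Section 11.1 gives 35 patients instead of 30; the argument does not depend on which applies. Assumptions: exponential PFS, 30.4375 days per month, scans on their due date, no unscheduled scans, and no deaths before scan detection.

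**The plan's own figures.** 0.5^(12/5) = 18.9% and 0.5^(12/9) = 39.7%, matching 19% and 40%. By normal approximation, n = [(1.2816·√(0.19·0.81) + 1.2816·√(0.40·0.60))/0.21]² = 28.98, so 29; at n=30 the power is 90.7%. The stated design is reproduced. The documents give no rejection count. By exact binomial at n=30, 9 or more successes has size 0.1004 and power 0.906; 10 or more has size 0.045 and power 0.824. I use 10 or more, the count that keeps within 10%.

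**Scan dates.** Nominal scans fall on days 84, 168, 252 and 336. Slack before month 12 is 365 − 336 = 29 days.

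- One 21-day delay: 336 + 21 = day 357, still before month 12.
- Two 21-day delays: 336 + 42 = day 378, past it.
- Twelve cycles at +3 days: 12 × 31 = day 372, but only if the window runs from the previous injection, which the text does not settle.

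Once scan 4 passes day 365, scan 3 is the last scan before month 12. It lies between day 252 (all slip after scan 3) and day 294 (two full delays before it).

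**Null rate as read at the last scan**, S(t) = 0.5^(t/(30.4375 × 5)):

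| Last scan by month 12 | Day | S(t) |
|---|---|---|
| Scan 4, no delay | 336 | 21.6% |
| Scan 4, one 21-day delay | 357 | 19.7% |
| Scan 3, no slip by then | 252 | 31.7% |
| Scan 3, 14 days' slip (assumed mid case) | 266 | 29.8% |
| Scan 3, two full delays | 294 | 26.2% |

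**False-positive probability.** Let a share f be read at scan 3 and everyone else at day 336: p = (1 − f)·0.2165 + f·S(scan 3), then P(X ≥ 10 | 30, p). The documents give no delay frequency, so f is an assumption.

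| f | p, scan 3 at day 266 | P(X ≥ 10) | Range, scan 3 at day 294 to 252 |
|---|---|---|---|
| 0 | 0.2165 | 0.095 | |
| 10% | 0.2246 | 0.116 | 0.107 to 0.121 |
| 20% | 0.2327 | 0.139 | 0.119 to 0.151 |
| 30% | 0.2408 | 0.165 | 0.132 to 0.185 |

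With 9 or more, the mid-case figures are 0.184 undelayed and 0.216, 0.249 and 0.285.

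**Offset from smaller slips.** Suppose 10% pass month 12 (scan 3 at day 266), 40% have one 21-day delay and 50% have none: p = 0.1·0.2977 + 0.4·0.1967 + 0.5·0.2165 = 0.2167. P(X ≥ 9) is 0.185 against 0.184 undelayed; P(X ≥ 10) is 0.096 against 0.095. About four single-delay patients cancel one who passes month 12: (0.2977 − 0.2165)/(0.2165 − 0.1967) ≈ 4.1.

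**Mean recorded PFS under the null.** With the first scan on day a and then one every 84 days, the mean is a + S(a)·84/(1 − S(84)). For a = 84 this is 8.68 months. For a = 105 (one delay before the first scan) it is 8.83, and for a = 114 (30 days in total) 8.91. The patient gains 0.15 to 0.23 month. If 20% of patients are delayed, the trial average moves 0.2 × 0.15 = 0.03 to 0.2 × 0.23 ≈ 0.05 month.

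**The case against.** The strongest reply is that the drift is small and does not run in one direction. A reader might infer that any dose delay flatters the drug at month 12. The dates do not support that: a single maximal delay brings scan 4 closer to month 12 and lowers the null reading from 21.6% to 19.7%, nearer the planned 19%. With enough such patients, the net effect on the false-positive probability is about nil. This part of the reply stands, and it limits the size of the point.

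A reader might also infer that delays come mainly from toxicity, so that the drift rewards a toxic drug. The documents do not show this. Table 6-2 and section 6.3.2 respond to events by dose reduction or discontinuation, and section 6.3.1 specifies no hold for hyperglycaemia. The liver rule in 6.3.3 ends treatment if enzymes have not recovered after two weeks, or if they rise again after resumption. It therefore cannot produce repeated delays, and a two-week hold between 28-day injections need not delay a dose at all. Delays may follow toxicity, but the general 21-day allowance is not tied to it.

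Two further limits stand. Accumulating the +3-day window over twelve cycles is an extreme case, since the window is symmetric and 6.3 refers to an intended dosing day. Section 11.2 also plans an exponential-based lower bound if a preliminary test permits; there the step back to scan 3 does not apply, and only the slight lengthening of recorded PFS matters.

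None of this supplies a calendar anchor. The scan date still depends on the dose date.

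**Conclusion.** The point holds as a scheduling weakness of modest and uncertain size. Before year 5, scan dates depend on injection dates, so recorded PFS partly reflects dose timing. For a patient delayed early, mean recorded PFS lengthens by about 0.15 to 0.23 month under the null. The 12-month rate is biased upward only through patients whose total slip exceeds 29 days, which takes at least two delays or one delay plus window drift. Smaller slips bias it slightly downward.

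The rise from 0.095 to 0.116, 0.139 or 0.165 rests on assumed shares of 10%, 20% and 30%, on no other patient being delayed, on exponential PFS with a 5-month median, and on a rejection count that the documents do not state. It shows what the text allows and is not a forecast. The documents support neither a general bias in the drug's favour nor a claim that toxicity is the main cause of delay. The correction is still worth making, because it is cheap and removes a dependence that a single-arm comparison cannot absorb.

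**What to change.** In section 7.2, Table 7-3 and footnote h, schedule radiologic assessment every 12 weeks (84 days, with a fixed window such as ±7 days) from the date of first study treatment, regardless of dose delays or interruptions, while the patient remains on study treatment. Convert the six-cycle interval after two years to 24 weeks. Reconcile the 12-cycle and 12-month wordings after year 5, which differ by 365 − 336 = 29 days.

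The cost is amendment wording, and a scan that may fall on a different day from a delayed injection visit. Limiting the rule to patients on treatment avoids implying extra scans after discontinuation, where Table 8.4 censors. No dosing rule changes, and neither does the sample size.

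The change makes the read-out the same for every patient; it does not bring it to month 12. Scan 4 stays nominally at day 336, where the null reads 21.6%, and patients with small slips lose their incidental move towards month 12. That mismatch is a separate issue and needs its own remedy.

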7.3 End of Treatment Evaluation

Data to be obtained at completion of study:

- Physical examination
- Toxicity assessment
- Vital signs
- Weight
- ECOG PS
- CBC with differential
- Comprehensive metabolic panel
- Glycosylated hemoglobin
- ECG
- Assessment of adverse events
- Radiologic assessment of tumor burden (if patient is discontinued for any reason other than radiographic disease progression).

Table 7-3 lists all of the assessments and indicates the visits at which they are to be performed with an “X”. All data obtained from these assessments must be supported in the patient’s source documentation.

Table 7-3 Visit evaluation schedule

Evaluation	Screening/ Baseline^a	6 hours after 1st injection, 21 days after 1st and 3rd injections	Each Cycle (day 1)^k	Cycle 6	Every 3 Cycles	End^b
Informed consent	X					
Demographics	X					
Relevant medical history/ current medical conditions	X		X			X
Diagnosis and extent of cancer	X					
Physical exam	X		X			X
Vital signs	X		X			X
ECG ^c	X	X		X	X	X
LFT testing		X				
ECOG Performance Status	X		X			X
CBC with differential ^d	X		X			X
Glycosylated hemoglobin	X					X
Fasting	X		X			X

Comprehensive metabolic panel ^e						
Pregnancy test and review of contraception ^f	X					X
Secretory hormones ^g and serum chromogranin A	X				X	
Radiologic assessment of tumor burden ^h	X				X	X
Adverse events ⁱ	X		X			X
Concomitant medications ^j	X		X			X
EORTC QLQ C-30 and EORTC QLQ GI-NET21 questionnaires	X				X	

^a Screening includes review of: demography/informed consent, inclusion/exclusion criteria, relevant medical history/concomitant medications, diagnosis and extent of cancer.

^b Patients who interrupt or permanently discontinue pasireotide due to an adverse event or abnormal laboratory value must be followed at least weekly for 28 days after the last dose of SOM230, and subsequently at monthly intervals until resolution or stabilization of the event, whichever comes first.

^c All ECGs should be done before SOM230 injection on the same day. ECG should be done at any time when clinically indicated.

^d Complete blood count must include: hemoglobin, hematocrit, platelets, total white blood cell count and differential.

^e Comprehensive metabolic panel should include fasting glucose, sodium, potassium, chloride, bicarbonate, creatinine, blood urea nitrogen, albumin, total protein, SGOT (AST), SGPT (ALT), total bilirubin, alkaline phosphatase, calcium and magnesium. Patients are to fast overnight for 8 hours prior to all biochemistry samples being taken. Blood samples are to be taken in the morning. Water is allowed during this time. Clinically significant electrolyte abnormalities are to be addressed prior to each SOM230 administration.

^f For women of child-bearing potential: Women of childbearing potential must have a negative serum pregnancy test within 14 days of enrollment. Acceptable contraception must be used while on study and for at least 60 days after last dose of pasireotide.

^g If patients present with hormonally active tumor, secretory hormone levels corresponding to the syndrome (e.g. urine 5-HIAA, gastrin, glucagon, insulin, etc.) should be measured at baseline and each restaging cycle.

^h Baseline radiologic tests (CT or MRI with iv contrast) should include all known sites of metastatic disease. For most midgut carcinoid tumors, a CT or MRI scan of the abdomen and pelvis is indicated. For pancreatic neuroendocrine tumors, a CT or MRI scan of the abdomen may be sufficient. Patients who have been on study for > 2 years will undergo scans every 6 cycles. Patients who have been on study for > 5 years will undergo scans every 12 cycles.

ⁱ See section 9.1 for definitions of adverse events

^j All concomitant medications, including over the counter drugs, should be documented each visit. Particular attention should be paid to dose of diabetic medications. Patients with diabetes are to be instructed to check blood glucose levels via a fingerstick several times daily, particularly for the first few days of treatment.

^k For patients who have been on study for >5 years, all procedures, with the exception of vitals and treatment administration, will occur only once every 6 months (EP, labs, EKGs, questionnaires); scans will occur once every 12 months.

8 Outcome Measures

The primary efficacy endpoint is progression-free survival, defined as the time from the date of first study treatment to the date of the first documented disease progression (by RECIST criteria) or death due to any cause. If a patient has not progressed or died at the date of the analysis cut-off or when he/she receives any further anti-cancer therapy, PFS is censored at the time of the last tumor assessment before the cut-off or the anti-cancer therapy date.

